12.8.3 Evaluation of organ enlargement³²

Complete Response (CR): Regress to normal

Partial response (PR): Spleen must have regressed by >50% in length beyond normal

Stable Disease (SD): No increase consistent with progression

Progressive Disease (PD): In the setting of splenomegaly, the splenic length must increase by 50% of the extent of its prior increase beyond baseline. If no prior splenomegaly, must increase by at least 2 cm from baseline.

New or recurrent splenomegaly

12.9 Best Response

Two objective status determinations of disease status, obtained on two consecutive

determinations, separated by at least a 3 week time period, are required to determine the patient's overall best response. Two objective status determinations of CR before progression are required for best response of CR. Two determinations of PR or better before progression, but not qualifying for a CR, are required for a best response of PR. Two determinations of stable/no response or better before progression, but not qualifying as CR or PR, are required for a best response of stable/no response; if the first objective status is unknown, only one such determination is required. Patients with an objective status of progression on or before the second evaluations (the first evaluation is the first radiographic evaluation after treatment has been administered) will have a best response of progressive disease. Best response is unknown if the patient does not qualify for a best response of progressive disease and if all objective statuses after the first determination and before progression are unknown.

12.9.1 **Evaluation of Best Overall Response**

The best overall response is the best response recorded from the start of the treatment until disease progression/recurrence (taking as reference for progressive disease the smallest measurements recorded since the treatment started). The patient's best response assignment will depend on the achievement of both measurement and confirmation criteria.

Table 5. Sequences of overall response assessments with corresponding best response.

1 st Assessment	2 nd Assessment	Best Response
Progression		Progressive disease
Stable, PR, CR	Progression	Progressive disease
Stable	Stable	Stable
Stable	PR, CR	Stable
Stable	Not done	Not RECIST classifiable
PR	PR	PR
PR	CR	PR
PR, CR	Not done	Not RECIST classifiable
CR	CR	CR

12.9.2 **Duration of Response**

Duration of overall response: The duration of overall response is measured from the time measurement criteria are met for CR or PR (whichever is first recorded) until the first date that recurrent or progressive disease is objectively documented (taking as reference for progressive disease the smallest measurements recorded since the treatment started).

The duration of overall CR is measured from the time measurement criteria are first met for CR until the first date that progressive disease is objectively documented.

Duration of stable disease: Stable disease is measured from the start of the treatment until the criteria for progression are met, taking as reference the smallest measurements recorded since the treatment started, including the baseline measurements.

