Circulating Tumor DNA (ctDNA-optional) ⁹			Cycle 5, Day 1 and (for patients receiving \geq 5 cycles only) at end of Protocol Therapy OR disease progression

[^] Studies may be obtained within 72 hours prior to the start of the subsequent cycle.

- 1 Women of childbearing potential require a negative pregnancy test prior to starting treatment; sexually active patients must use an acceptable method of birth control. Abstinence is an acceptable method of birth control.
- 2 If patients have Grade 4 neutropenia then CBCs should be checked at least every other day until recovery to Grade 3 or until meeting the criteria for dose limiting toxicity.
- 3 If patients develop Grade 3 or higher thrombocytopenia then CBCs should be checked every 3-4 days until recovery per [Section 6.1](#)
- 4 Tumor Disease Evaluation should be obtained on the next consecutive cycle after initial documentation of either a PR or CR. Subsequent scans may restart 2 cycles after the confirmatory scan. If the institutional investigator determines that the patient has progressed based on clinical or laboratory evidence, he/she may opt not to confirm this finding radiographically.

4-A Neurological exam also required for CNS patients

4-B Non- Hodgkin Lymphoma/ Histiocytosis patients are required to have PET scans within 2 weeks prior to start of therapy and should also be followed with PET scans if positive at diagnosis. Refer to [Section 12.8](#)

4-C Patients with neuroblastoma must have both CT/MRI and MIBG scintigraphy prior to enrollment if the patient was enrolled with or has a history of having MIBG avid tumor. Otherwise the patient must have both CT/MRI and bone scan prior to enrollment. For patients with neuroblastoma and measurable disease by CT or MRI, lesions should be measured and followed using the same modality (CT or MRI) in addition to MIBG or bone scan. For patients with neuroblastoma and evaluable disease by MIBG scintigraphy or bone scan, use the same modality (MIBG scintigraphy or bone scan) to image and follow patients; CT/MRI are not required but may be performed as

clinically indicated. Refer to [Section 12.5.4](#) and [Section 12.9](#)

- 5 Bone marrow aspirate and/or biopsy only required in patients suspected of having bone marrow metastasis on the basis of history, symptoms, laboratory evaluation or other clinical data. Should only be performed on patients with known bone marrow involvement at baseline.

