11.4 Methods of Analysis

Response criteria are described in Section 12. A responder is defined as a patient who achieves a best response of PR or CR on the study. Response rates will be calculated as the percent of evaluable patients who are responders, and confidence intervals will be constructed using the Wilson score interval method.³⁰ Decision making for A'Hern design cohorts will follow rules described above.

Any responses or lack thereof in patients enrolled during the determination of the Recommended Phase 2 Dose (dose finding phase) will count toward the objective response rate in their respective cohort.

Toxicity tables will be constructed to summarize the observed incidence by type of toxicity and grade. A patient will be counted only once for a given toxicity for the worst grade of that toxicity reported for that patient. Toxicity information recorded will include the type, severity, time of onset, time of resolution, and the probable association with the study regimen.

11.5 **Evaluability for Response**

Any eligible patient who is enrolled and receives at least one dose of protocol therapy will be considered evaluable for response. Any patient who receives non-protocol anti-cancer therapy during the response evaluation period will be considered a non-responder for the purposes of the statistical rule, unless they show an objective response prior to receiving the non-protocol anti-cancer therapy (in which case they will be considered a responder). Patients who demonstrate a complete or partial response confirmed by central review will be considered to have experienced a response. When opening expansion cohorts, the evaluation period for determination of best response will be 6 treatment cycles. All other patients will be considered non-responders. Patients who are not evaluable for response evaluation may be replaced for the purposes of the statistical rule. All patients considered to have a response (CR or PR) must have imaging studies reviewed centrally at the COG. Centers will be notified by the COG about requests for scans of patients with stable disease. Preliminary assessment of activity using institutionally provided tumor measurements will be entered into CDUS quarterly. The central review by COG will be provided as the final reviewed assessment of response when such becomes available.

11.6 **Evaluability for Toxicity**

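### Read literally, Table 5 gives best response Stable to a patient who is stable at the first scan and has a later, confirmed PR or CR, whom the Section 12.9 text counts as a responder

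*Combined protocol and SAP*

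**What the plan says.** Section 11.4 rests the primary endpoint on best response: "A responder is defined as a patient who achieves a best response of PR or CR on the study". Section 11.3.1 declares success with at least 3 responders among 20 evaluable patients. Sections 12.4.4, 12.5.5, 12.6.2 and 12.7.7 all refer to Section 12.9 for best response. Section 12.8 (lymphoma and histiocytosis) does not.

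The Section 12.9 text sets these rules:
- For PR: "Two determinations of PR or better before progression, but not qualifying for a CR, are required for a best response of PR".
- For CR: "Two objective status determinations of CR before progression are required for best response of CR".
- For stable disease: "Two determinations of stable/no response or better before progression, but not qualifying as CR or PR, are required for a best response of stable/no response".

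None of these is tied to particular scans. Section 12.9.1 adds that best overall response is taken over the period from start of treatment to progression or recurrence, and that it depends on confirmation.

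The table follows in the same subsection, captioned "Table 5. Sequences of overall response assessments with corresponding best response". It has columns for a 1st and a 2nd assessment and one for best response. The row at issue reads "Stable PR, CR Stable", that is, 1st Stable, 2nd PR or CR, best response Stable. PR or CR results only where the 1st assessment is already PR or CR. Section 12.9 also fixes what counts as first: "the first evaluation is the first radiographic evaluation after treatment has been administered".

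On timing, Section 5.1 schedules evaluations at the end of every other cycle three times, then every third cycle. Footnote 4 to the Section 8.1 table says "Tumor Disease Evaluation should be obtained on the next consecutive cycle after initial documentation of either a PR or CR", and Section 12.3 repeats the requirement.

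**The concern.** The scan schedule can readily produce a sequence that the text and the table classify differently. A patient who is stable at the first scan, responds at the second and has the response confirmed at the third meets the text rule for PR. The first two assessments of that patient sit on a Table 5 row that ends in Stable, and no row lets the third scan change the result.

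The consequence is a responder count that depends on which half of Section 12.9 the analyst uses. Two people working correctly from the same scans could report 3 of 20 and 2 of 20, which are opposite conclusions on the primary aim. Opening an expansion cohort (Section 11.3.2) is exposed in the same way, since it needs 3 responders with one histology. Choosing between the two rules once the scans are known would be a post hoc decision.

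**Working it through.** **Classifying the sequences.** Under Section 5.1 the first three scheduled scans fall at the end of Cycles 2, 4 and 6. A response first seen at Cycle 4 is confirmed at Cycle 5, and one first seen at Cycle 6 is confirmed at Cycle 7. Consecutive 28-day cycles meet the 3-week minimum separation in Section 12.9.

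| Sequence | Section 12.9 text | Table 5 read literally |
|---|---|---|
| SD, PR, no later assessment | Stable (only one PR determination) | Stable |
| SD (C2), PR (C4), PR (C5) | PR | Stable |
| SD (C2), SD (C4), PR (C6), PR (C7) | PR | Stable (row Stable, Stable) |
| PR, CR | PR | PR |

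Text and table agree on the first and last lines and differ on the two middle ones.

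**Is the table tied to scans 1 and 2?** Its column heads say 1st and 2nd. Its row for Stable, PR or CR followed by Progression returns progressive disease, which matches the text rule for progression at or before the second evaluation. Treating the rows as a pair that moves along the sequence would need a further rule on which pair wins. Otherwise PR, PR, progression would also meet the progression row through its last two scans. The protocol contains no such rule.

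**The plan's own figure.** Inputs from Section 11.3: N = 20, success at 3 or more, null rate 5%, target rate 25%, stated alpha 10% and power 90%.

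P(X ≥ 3) = 1 − Σ(k = 0 to 2) C(20, k) p^k (1 − p)^(20 − k)

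- p = 0.25: 1 − (0.0032 + 0.0211 + 0.0669) = 0.909, which reproduces the stated 90%.
- p = 0.05: exact type I error 0.075, below the nominal 10% ceiling.

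**Effect of literal use of the table.** Let f be the share of true responders whose first PR or CR comes at the second scan or later. The documents give no value, so f is an assumption. The countable rate is p × (1 − f). The last column assumes the same share among responders at the 5% null rate.

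| f (assumed) | Countable rate at 25% | Power | Exact alpha |
|---|---|---|---|
| 0 | 25.0% | 0.909 | 0.075 |
| 20% | 20.0% | 0.794 | 0.044 |
| 30% | 17.5% | 0.706 | 0.031 |
| 40% | 15.0% | 0.595 | 0.021 |
| 50% | 12.5% | 0.465 | 0.013 |

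If the Section 12.9 text is followed, the first line applies whatever f is. Without any assumption about f, moving one patient turns 3/20 (rule met) into 2/20 (rule not met).

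**The case against.** The best defence is that Table 5 is incomplete and does not contradict the text. For a patient with exactly two assessments, SD then PR, the text also gives Stable, because there is only one PR determination. The disagreement appears only when a two-assessment row is applied to a three-assessment sequence.

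The surrounding provisions also favour counting the later response. The 12.9 text keeps Stable for patients who do not qualify as CR or PR, and the 12.9.1 lead-in runs to progression. Sections 11.5 and 12.3.1.1 count a centrally confirmed CR or PR as a response without restricting which scan shows it. Section 11.5 allows 6 cycles for best response when expansion cohorts are opened, which is beyond the second scheduled scan. The confirmatory scan is ordered whenever a response first appears.

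Most of this stands. The row is correct for an unconfirmed response, and an analyst who reads these sections together would reach the right count. What remains is that the table column is headed as best response, its assessments are numbered from the first on-treatment scan, and nothing says the text prevails over the table.

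A reader might go further and infer that the plan limits the primary endpoint to responses present at the first scan, or that the response rate will be biased downward. The documents do not support that, because it requires the table to override the text, Section 11.5 and Section 12.3.1.1. Nor do they say that the schedule or the 2-year treatment limit was chosen to capture slow responses.

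**Conclusion.** There is an internal contradiction in the rule that determines responder status, and it should be fixed. It concerns patients whose PR or CR first appears after the first on-treatment scan and is then confirmed, in the tumor categories that refer to Section 12.9. One such patient could decide the 3-of-20 rule.

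The loss of power, from 0.91 to between 0.79 and 0.46, rests on two conditions: that the table is applied literally, and that 20% to 50% of responders are late. The first is not the better reading of the protocol as a whole, and the second is an assumption. The direction is conservative: literal use under-counts responders and lowers the type I error, so it cannot produce a false success. The row PR then CR = PR has no effect on the response rate, since both count as response.

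**What to change.** In Section 12.9.1:
- State that the Section 12.9 text governs over the whole sequence of assessments before progression, and that Table 5 applies only where there are no later assessments.
- Limit the row Stable then PR or CR = Stable to a PR or CR that is not confirmed.
- Add rows for later confirmation, such as Stable, PR, then PR or CR = PR; and Stable, CR, CR = CR. Writing PR and CR separately avoids ambiguity over Stable, PR, CR.

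The cost is a sentence or two and a few table rows. No scans are added, because the confirmatory scan is already required, and the sample size and decision rule do not change. The wording should be settled before responses are classified.

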13.0 ADVERSE EVENT REPORTING REQUIREMENTS

Adverse event data collection and reporting which are required as part of every clinical trial, are done to ensure the safety of patients enrolled in the studies as well as those who will enroll in future studies using similar agents. Adverse events are reported in a routine manner at scheduled times during a trial. (Please follow directions for routine reporting provided in the Case Report Forms for this protocol). Additionally, certain adverse events must be reported in an expedited manner to allow for optimal monitoring of patient safety and care. The following sections provide information about expedited reporting.

Reporting requirements may include the following considerations: 1) whether the patient has received an investigational or commercial agent; 2) whether the adverse event is considered serious; 3) the grade (severity); and 4) whether or not hospitalization or prolongation of hospitalization was associated with the event.

An investigational agent is a protocol drug administered under an Investigational New Drug Application (IND). In some instances, the investigational agent may be available commercially, but is actually being tested for indications not included in the approved package label.

13.1 Expedited Reporting Requirements – Serious Adverse Events (SAEs)

Any AE that is serious qualifies for expedited reporting. An AE is defined as any untoward medical occurrence associated with the use of a drug in humans, whether or not considered drug related. A Serious Adverse Event (SAE) is any adverse drug event (experience) occurring at any dose that results in ANY of the following outcomes:

- 1) Death.
- 2) A life-threatening adverse drug experience.
- 3) An adverse event resulting in inpatient hospitalization or prolongation of existing hospitalization (for ≥ 24 hours). This does not include hospitalizations that are part of routine medical practice.
- 4) A persistent or significant incapacity or substantial disruption of the ability to conduct normal life functions.
- 5) A congenital anomaly/birth defect.
- 6) Important Medical Events (IME) that may not result in death, be life threatening, or require hospitalization may be considered a serious adverse drug experience when, based upon medical judgment, they may jeopardize the patient or subject and may require medical or surgical intervention to prevent one of the outcomes listed in this definition.

13.1.1 Reporting Requirements - Investigator Responsibility

Clinical investigators in the treating institutions and ultimately the Study Chair have the primary responsibility for AE identification, documentation, grading, and assignment of attribution to the investigational agent/intervention. It is the responsibility of the treating physician to supply the medical documentation needed to support the expedited AE reports in a timely manner.

Note: All expedited AEs (reported via CTEP-AERS) must also be reported via routine reporting. Routine reporting is accomplished via the Adverse Event (AE) Case Report Form (CRF) within the study database.

13.1.2 CTEP-AERS Expedited Reporting Methods

Expedited AE reporting for this study must only use CTEP-AERS (Adverse Event Expedited Reporting System), accessed via the CTEP home page <https://ctepcore.nci.nih.gov/ctepaers/pages/task>.

Send supporting documentation to the NCI by fax ([contact]) and by email to both [contact]

and to the APEC1621J COG Study Assigned Research Coordinator. **ALWAYS include the ticket number on all faxed and emailed documents.**

13.2 Steps to Determine If an Adverse Event Is To Be Reported In an Expedited Manner

Step 1: Identify the type of adverse event using the current version of the NCI CTCAEv5.0.

The descriptions and grading scales found in the current version of the CTCAEv5.0 will be used for AE reporting. All appropriate treatment areas should have access to a copy of the CTCAEv5.0. A copy of the CTCAEv5.0 can be downloaded from the CTEP website (<http://ctep.cancer.gov>).

Step 2: Grade the adverse event using the NCI CTCAEv5.0.

Step 3: Review [Table A](#) in this section to determine if:

- the adverse event is considered serious;
- there are any protocol-specific requirements for expedited reporting of specific adverse events that require special monitoring; and/or
- there are any protocol-specific exceptions to the reporting requirements.

- Any medical event equivalent to CTCAEv5.0 grade 3, 4, or 5 that precipitates hospitalization (or prolongation of existing hospitalization) must be reported regardless of attribution and designation as expected or unexpected with the exception of any events identified as protocol-specific expedited adverse event reporting exclusions.
- Any event that results in persistent or significant disabilities/incapacities, congenital anomalies, or birth defects must be reported via CTEP-AERS if the event occurs following treatment with an agent under a CTEP IND.
- Use the NCI protocol number and the protocol-specific patient ID provided during trial registration on all reports.
- As referenced in the CTEP Adverse Events Reporting Requirements, an AE that resolves and then recurs during a subsequent cycle does not require CTEP-AERS reporting unless (1) the Grade increases; or (2) hospitalization is associated with the recurring AE.
- Some adverse events require notification **within 24 hours** (refer to Table A) to NCI via the web at <http://ctep.cancer.gov> (telephone CTEP at: **[contact]** within 24 hours of becoming aware of the event if the CTEP-AERS 24-Hour Notification web-based application is unavailable). Once internet connectivity is restored, a 24-hour notification phoned in must be entered electronically into CTEP-AERS by the original submitter at the site.
- When the adverse event requires expedited reporting, submit the report **within 5 or 7 calendar days** of learning of the event (refer to Table A).

Table A: Phase 1 and Early Phase 2 Studies: Expedited Reporting Requirements for Adverse Events that Occur on Studies under an IND/IDE within 30 Days of the Last Administration of the Investigational Agent/Intervention ^{1,2}

FDA REPORTING REQUIREMENTS FOR SERIOUS ADVERSE EVENTS (21 CFR Part 312)

NOTE: Investigators **MUST** immediately report to the sponsor **ANY** Serious Adverse Events, whether or not they are considered related to the investigational agent(s)/intervention (21 CFR 312.64)

An adverse event is considered serious if it results in **ANY** of the following outcomes:

- 1) Death
- 2) A life-threatening adverse event
- 3) An adverse event that results in inpatient hospitalization or prolongation of existing hospitalization for ≥ 24 hours
- 4) A persistent or significant incapacity or substantial disruption of the ability to conduct normal life functions
- 5) A congenital anomaly/birth defect
- 6) Important Medical Events (IME) that may not result in death, be life threatening, or require hospitalization may be considered serious when, based upon medical judgment, they may jeopardize the patient or subject and may require medical or surgical intervention to prevent one of the outcomes listed in this definition. (FDA, 21 CFR 312.32; ICH E2A and ICH E6).

ALL SERIOUS adverse events that meet the above criteria **MUST** be immediately reported via CTEP-AERS within the timeframes detailed in the table below.

Hospitalization	Grade 1 and Grade 2 Timeframes	Grade 3-5 Timeframes
Resulting in Hospitalization ≥ 24 hrs	7 Calendar Days	24-Hour 5 Calendar Days
Not resulting in Hospitalization ≥ 24 hrs	Not required	

NOTE: Protocol specific exceptions to expedited reporting of serious adverse events are found in the Specific Protocol Exceptions to Expedited Reporting (SPEER) portion of the CAEPR.

Expedited AE reporting timelines are defined as:

- “24-Hour; 5 Calendar Days” - The AE must initially be reported via CTEP-AERS within 24 hours of learning of the AE, followed by a complete expedited report within 5 calendar days of the initial 24-hour report.
- “7 Calendar Days” - A complete expedited report on the AE must be submitted within 7 calendar days of learning of the AE.

¹Serious adverse events that occur more than 30 days after the last administration of investigational agent/intervention and have an attribution of possible, probable, or definite require reporting as follows:

Expedited 24-hour notification followed by complete report within 5 calendar days for:

- All Grade 3, 4, and Grade 5 AEs

Expedited 7 calendar day reports for:

- Grade 2 AEs resulting in hospitalization or prolongation of hospitalization

² For studies using PET or SPECT IND agents, the AE reporting period is limited to 10 radioactive half-lives, rounded UP to the nearest whole day, after the agent/intervention was last administered. Footnote “1” above applies after this reporting period.

Effective Date: May 5, 2011

13.3 Additional Instructions or Exceptions to CTEP-AERS Expedited Reporting Requirements:

- Myelosuppression, (Grade 1 through Grade 4 adverse events as defined in the table below), does not require expedited reporting, unless it is associated with hospitalization.

Category	Adverse Events
INVESTIGATIONS	Platelet count decreased
INVESTIGATIONS	White blood cell decreased
INVESTIGATIONS	Neutrophil count decreased
INVESTIGATIONS	Lymphocyte count decreased
BLOOD/LYMPHATICS DISORDERS	Anemia

- See also the Specific Protocol Exceptions to Expedited Reporting (SPEER) in [Section 9.1.9](#) of the protocol.

